2.0 Objectives*

- 2.1 The purpose of this study is to measure neural and biomarker correlates of vagal nerve stimulation (VNS) in men and women with a history of Opioid Use Disorders (OUDs). In the UG3 phase we will have two studies, Study #1 will be to optimize dosing (N=20) and Study #2 to measure brain and biological correlates of nVNS versus sham in conjunction with exposure to drug use cues (N=20). We will proceed to the UH3 phase which is a larger study in OUD patients if the goals of the UG3 phase are met per NIDA. Only the UG3 phase is covered here.
- 2.2 Brain function will be measured with positron emission tomography (PET) and biomarkers will be measured in blood, with an assessment of a broad range of stress responsive sympathetic, hormonal and immune markers
- 2.3 We hypothesize a decrease in sympathetic function and enhanced anterior cingulate function with VNS.

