5.0 Study Intervention/Investigational Agent

- 5.1 Description: This study assesses nVNS versus a sham stimulation effects on behaviors of drug craving with and without exposure to

PROTOCOL TITLE: Non-invasive Vagal Nerve Stimulation in Opioid Use Disorders

drug cues as well as brain response, neurophysiology and biomarkers. NVNS is applied to the neck and electrically stimulates one of the cranial nerves (the vagus) as it passes through the carotid sheath, exerting effects centrally in the brain and peripherally on autonomic and inflammatory function

- 5.2 Drug/Device Handling: Active nVNS and sham control are kept by research staff under lock and key and only used for the purposes of the study under supervision of the research coordinator.
- 5.3 The nVNS device has been approved by the Emory IRB for use in a current study in patients with PTSD. It is non-invasive with minimum side effects and has been shown to be well tolerated and there have been no adverse events or untoward effects in 56 subjects to date.

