6.4 Magnetic Resonance Imaging (MRI) of the Brain: Subjects in both Study #1 and Study #2 will undergo MRI brain imaging at CSI for identification of the vagus nerve in the neck. Sequences to be obtained include volumetric interpolated breath-hold examination (VIBE), TR=4.93, TE=2.46, flip angle=9, Field of View 210 mm, 112 slices, voxel .78 x .78 x .8, averages 3, time of acquisition 4:38. 3D constructive interference in steady state (CISS), TR=5.46, TE=2.43, flip angle=42, Field of View 152 mm, 112 slices, voxel .6 x .6 x .6, averages 1, time of acquisition 5:17.

6.5

For Study #2 we look at physiology with nVNS or sham in OUD patients. Brain function will be measured with high resolution positron emission tomography (HR-PET) (264-270), autonomic function with wearable sensing devices, and biomarkers will be measured in blood, with an assessment of a broad range of stress responsive sympathetic, hormonal and immune markers. A

complete outline of study procedures for Study #2 is presented in Figure 4.

After initial set up and rest period subjects will rest for 30 min. Next, subjects will undergo a series of viewing exercises while lying in the High Resolution Positron Emission Tomography (HR PET) scanner with physiologic monitors attached. After an initial baseline period of resting (condition 1), the subjects will then view two neutral 120 second videos (condition 2), followed by a playback of two opioid use related videos (condition 3). The subject will be instructed to image each event as vividly as possible. VNS or sham will be randomized and given during exposure to the videos. For two of the scans, we are looking at effects of nVNS on the brain with no intervention. The subjects will undergo nVNS vs. Sham VNS stimulation as per published methods (see above).

The VAS and SUDS and other behavioral measures are assessed in the beginning and after each task to assess the efficacy of the

[figure not shown]

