- H₂[15O] and PET: H₂[15O] or radiolabeled water has been administered to thousands of subjects without side effects or toxicity to date at the doses to be used in this study. [name] holds an IND for use of radiolabeled water at Emory University. H₂[15O] is a radioactive materials. Each patient will have eight H₂[15O] blood flow scans. For each O-15 water scan 20 mCi of H₂[15O] will be injected as an intravenous bolus. The body organs which receive the highest dose of H₂[15O] is the intestine and gonads. The radiation dose to body organs in this study is well within the Food and Drug Administration (FDA) national guidelines for radiation exposure for human research studies and less than the total amount that is permitted for research studies in one year. Risk will be reduced by careful screening. The subjects will be asked if they have participated in research studies that involved radiation over the past year. Risks are reduced by the principles of ALARA, or As Low As Reasonably Allowable, which involves time (reducing time exposure), distance (keeping dose away from subject) and shielding (using lead shields to protect from radiation as much as possible). Risk will also be reduced by ensuring radiation administration is not greater than that outlined in the protocol, and which is below limits for a single session set by regulatory agencies, and that subjects do not participate in more than three research sessions with radiation in a 12 month period, also per guidelines. Also, they will be advised that they should not participate in other research studies involving radioactivity over the next year without consulting [name] first. There is a small risk of claustrophobia with PET. If needed the study will be stopped.
- MRI: Subjects can become claustrophobic in the scanner. If needed the study can be stopped or 1-2 mg lorazepam given by mouth. If there is indwelling metal in the head this can cause injury. Subjects will be screened for indwelling metal.
- Opioid Use Related Videos: Viewing videos about opioid use may result in an increase in opioid craving. Viewing videos on smart glasses may cause wooziness or motion sickness. The research staff will debrief subjects, which involves talking about the experiences and helping

[figure not shown]
PROTOCOL TITLE: Non-invasive Vagal Nerve Stimulation in Opioid Use Disorders

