17.0 Data Management* and Confidentiality

17.1 We will use analysis of variance models with change in blood flow as dependent variable and absolute blood flow during control task as well as study group as explanatory variables. This analysis will assess differences in brain function according to diagnosis correcting for potential differences in baseline (control task) values. The ANOVA model will be blocked by the matching factor of past alcohol exposure. Analyses will be adjusted for whole brain blood flow. Additional control factors, including patients' age, age of onset of traumatization, years of education, IQ, OUD symptom level and duration of disease, use of oral contraceptive birth control, and smoking, will be entered in the model if they are significantly different between the study groups at an alpha level of 0.25, and/or if they are found to be confounders in the analysis, i.e., if they cause a change of >10% in the parameter estimate for study group when entered in the model. Adjusted means of blood flow will be computed for each combination of group and task to better describe the results. Point estimates and confidence intervals for the difference between groups will be assessed before and after including the covariates mentioned above in the model. Additional analyses will compare OUD patients with and without a history of co-morbid depression.

In all these analyses linear model assumptions, adequacy of fit, and presence of outliers will be checked by inspecting residual plots and influence statistics. Collinearity for variables included in the model will also be checked. Appropriate remedies will be applied, if necessary, to improve model fit and minimize collinearity.

Additional exploratory analyses will use subtraction analysis techniques to look for additional areas of activation for the purpose of generating hypotheses for future studies. Images of absolute blood flow will be subjected to a subtraction type analysis. Images will be realigned to the first image in the series and warped into a common anatomical space using methods described in the preliminary results. Images will be then analyzed using the general linear model of Friston for statistical analysis. The mean of blood flow scans within condition will be calculated and comparisons performed between conditions to assess blood flow with the condition. Areas of increased and decreased blood flow within patient group will be examined, as well as the interaction between

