PROTOCOL TITLE: Non-invasive Vagal Nerve Stimulation in Opioid Use Disorders

condition and diagnostic group. Images of t statistic will be created and surveyed for hypothesized regions (i.e. medial prefrontal cortex) where uncorrected z score values are greater than 2.86 (corresponding to a corrected p value of > 0.005).

Calculation of Sample Size

For calculation of sample size needed for PET measurement of anterior cingulate activation, we used values for blood flow in the amygdala (scaled to whole brain blood flow) based on previous pilot data. Fear-related tasks resulted in a $6.9 + 4.8\%$ increase in amygdala blood flow versus $1.2 + 1.4\%$ in controls (effect size 1.39). With two tails, an alpha value set at 0.05 and a power of 0.80, 10 subjects are needed in each group (VNS v sham) to show a significant difference between patients and controls (i.e. group by condition interaction). The number of subjects in each group will therefore be adequate to answer the questions proposed in this study.

- 17.2 All study staff will take required training prior to working with participants and/or PHI. All data will be kept in either locked offices in secure buildings or online via Redcap or on a password restricted research server. A certificate of confidentiality will be in place. Confidentiality will be assured by the use of subject codes when possible rather than personal identifiers. After the study is completed, the study database will be secured, and information will only be entered using subject identifier codes rather than personal identifiers. Published results will be presented as group data, without identifiers.
- 17.3 A (bi) weekly meeting with the staff, Study Coordinator and the PI is held to discuss any issues that may arise. A review of data is done for accuracy and protocol compliance. Data collection forms are verified for accuracy before storing in database. Describe any procedures that will be used for quality control of collected data.
- 17.4 Describe how data or specimens will be handled study-wide:
 - Study ID, date of visit, and type of sample will be included for each specimen
 - Specimens will be stored in a -80 freezer at EP12 or RSPH
 - Specimens will be stored until they are fully utilized for testing
 - The [name] Lab and the study team will have access to the data and/or specimens

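### Section 17.1 plans no nVNS versus sham analysis for the two PET scans set aside for nVNS effects with no intervention, and the main model can miss a stimulation effect common to both video types

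*Combined protocol and SAP*

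**What the plan says.** **Scans and conditions.** Section 6.6 states "Each patient will have eight H₂[15O] blood flow scans" and "For each O-15 water scan 20 mCi of H₂[15O] will be injected as an intravenous bolus". Section 6.5 numbers three conditions: rest (1), neutral videos (2) and opioid videos (3). It then says "VNS or sham will be randomized and given during exposure to the videos", and next "For two of the scans, we are looking at effects of nVNS on the brain with no intervention". Those two scans get no condition number and no stated place in the sequence. Section 6.2 also pairs stimulation or sham with both neutral and drug use videos, and describes the neutral videos as the control.

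**Hypothesis and endpoint.** Section 2.3: "We hypothesize a decrease in sympathetic function and enhanced anterior cingulate function with VNS". Section 4.1 lists enhanced anterior cingulate function within the primary endpoint.

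**Analysis.** The main PET model in 17.1 has "change in blood flow as dependent variable and absolute blood flow during control task as well as study group as explanatory variables". It treats the control task as the baseline and tabulates adjusted means by group and task. The exploratory maps compare conditions, which 17.1 does not list, and examine an interaction between "condition and diagnostic group".

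**The concern.** A pair of scans acquired for a stated purpose should have a stated analysis. Here the purpose is the effect of stimulation on the brain, but no sentence in 17.1 says how the two arms will be compared on those scans.

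This is more than missing detail because of how the main model is built. Its reference, the control task, is itself recorded under nVNS or sham. If nVNS raises cingulate flow during neutral and opioid videos alike, the reference rises along with the task, and the model removes some or all of the effect. A null result could then be read as no cingulate effect of nVNS when the effect was absorbed by the covariate. Scans taken under stimulation and referred to rest do not have that weakness, yet no contrast by arm is planned for them. If one is chosen after unblinding with 20 subjects, it will carry little weight.

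**Working it through.** **1. The plan's own sample size.** Section 17.1 states effect size 1.39, two-sided alpha 0.05, power 0.80 and 10 per group. The two-sample t solution is n = 9.19, rounded up to 10 per group (the normal approximation gives 9). Power at 10 per group is 0.836 by the t calculation. The stated figure reproduces and is not in dispute. It was derived for amygdala flow in a fear-related task and for a group-by-condition contrast.

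**2. Share of the imaging.**
- Scans: 2 / 8 = 25%.
- Activity per subject: 2 × 20 = 40 mCi of 8 × 20 = 160 mCi.
- Over 20 completers: 2 × 20 = 40 of 8 × 20 = 160 scans.

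**3. What the planned analyses cover.**

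| Analysis in 17.1 | Scans it uses | Group term | Arm contrast for the two scans? |
|---|---|---|---|
| Main model | task and control task | study group | No |
| Adjusted means | group by task | study group, descriptive | No |
| Exploratory maps | conditions, not listed | diagnostic group | No |

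Section 10.2 requires OUD for entry to both studies, so diagnostic group has a single level and its interaction cannot be estimated.

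**4. What the main model does to a common effect.** Take the neutral videos as the control task, as 6.2 does. Let nVNS add δ to cingulate flow during both neutral and opioid videos, relative to sham.

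- Raw change: arm difference = δ − δ = 0.
- With control-task flow as covariate: arm coefficient = (arm difference in task flow) − b × (arm difference in control-task flow) = δ − bδ = (1 − b)δ, where b is the within-arm slope of task flow on control-task flow.

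The documents give no value for b, so a range is shown as an assumption:

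| b | Share of δ kept |
|---|---|
| 0 | 100% |
| 0.5 | 50% |
| 0.8 | 20% |
| 1 | 0% |

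The more closely a subject's flow in one video condition tracks flow in the other, the less of the effect survives.

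**5. The same formula with rest as covariate.** Rest is the initial period in 6.5, before the videos. With randomised arms and rest unstimulated, the expected arm difference in rest flow is 0. An effect δ in the two scans gives an arm coefficient of δ − b × 0 = δ, so nothing is lost.

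**6. Precision.** The documents give no effect size or SD for this contrast, so its power cannot be computed. With 10 per arm, an unadjusted two-sided t-test at 0.05 has 80% power only for a standardised difference of about 1.32 or more.

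**The case against.** **The cue-based model tests the stated aim.** Section 2.3 names no scan condition, and 2.1 and 6.2 describe Study #2 as nVNS versus sham combined with drug cues. This stands. A reader might infer that the two scans are the direct test of hypothesis 2.3, or that the plan never examines nVNS and the cingulate. Neither follows: the video scans also bear on the hypothesis, and the study-group term tests it for a cue-specific effect. What remains is that a common effect is attenuated.

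**The absence of a video is inferred.** The text says no intervention, directly after placing stimulation during the videos. Stimulation or sham without a video is the reading that best fits a sentence about effects of nVNS, but it is not stated. Figure 4, said to give the full outline, is not shown in the text reviewed. It may label the scans, but that would not add the contrast missing from 17.1.

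**Section 5.1 does not settle it.** It speaks of "nVNS versus a sham stimulation effects on behaviors of drug craving with and without exposure to" drug cues, which a reader might take as a call for a cue-free brain contrast. The phrase attaches to craving, and brain response is listed afterwards, so the point does not rely on it.

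**The exploratory maps could include these scans.** They are not limited to conditions 1 to 3, and diagnostic group looks like wording carried over from another study, since the sample-size paragraph also equates VNS versus sham with patients and controls. Read charitably, the maps might show an arm difference. As written, they define none.

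**Two larger numbers are tempting but unsupported.** Applying 1.39 at 10 per arm would suggest about 84% power for the new contrast, but that effect size belongs to a different region and task. Counting rest scans as unused too would raise the share to half, but the number of rest scans is not stated, and rest is a numbered condition that the exploratory comparisons can use.

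**Conclusion.** The point holds in this form. Two of eight PET scans (25%, 40 of 160 mCi per subject) are assigned to effects of nVNS with no intervention, are not listed as a condition, and have no nVNS versus sham analysis in 17.1. The main model keeps only (1 − b) of any cingulate effect common to both video types, and the raw change keeps none, although 2.3 and 4.1 concern enhanced cingulate function with VNS.

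Three assumptions carry this: the control task is the neutral video (supported by 6.2); stimulation or sham is given during both video types (6.2 and 6.5); and no intervention most likely means no video. The first two matter for the attenuation. The third affects only how the scans are described, since 17.1 names no arm contrast for them on any reading.

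This is a gap worth closing before unblinding in a small mechanistic study. It does not invalidate the cue-reactivity analysis.

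**What to change.** In 6.5, state what no intervention means for these two scans, give them a condition number and state their place in the scan order.

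In 17.1:
- Add one arm contrast, labelled secondary or exploratory: mean anterior cingulate flow over the two scans, nVNS versus sham, by ANCOVA with rest (condition 1) flow as covariate and the same whole-brain adjustment as the main model. Report the estimate and confidence interval.
- If the scans follow the opioid videos, note that the contrast with rest may include time or cue carry-over. Comparing the arms removes a drift common to both, but not carry-over that differs by arm.
- Replace diagnostic group with stimulation arm in the exploratory interaction, and list the conditions that enter it.

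The cost is a few sentences in 6.5, a paragraph in 17.1 and one model on data already being collected, with no new procedure. The downside is one more non-primary test, able to detect only large differences at 10 per arm.

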1.0 Study Summary

Study Title	Non-invasive Vagal Nerve Stimulation in Opioid Use Disorders
Study Design	Sham controlled, two groups
Primary Objective	Map physiology of vagal nerve stimulation in patients with OUDs
Secondary Objective(s)	Study #1 maps effect of varying durations of vagal nerve stimulation (nVNS) on craving and sympathetic function; Study #2 explores neurophysiology of nVNS or sham stimulation paired with drug cues.
Research Intervention(s)/ Investigational Agent(s)	Study #1 involves open label dose finding (varying durations of nVNS). Study #2 involves randomization to non-invasive vagal nerve stimulation (nVNS) or sham control stimulation with assessment of brain, behavioral, physiological, and biomarker responses to drug cues and/or craving.
IND/IDE #	IND 52220
Study Population	Men and women with a history of Opioid Use Disorders (OUDs)
Sample Size	N=20 for study 1 and n=20 for study 2
Study Duration for individual participants	2-3 study visits, 6 week follow up call
Study Specific Abbreviations/ Definitions	Non-invasive Vagal nerve stimulation (nVNS or VNS), Opioid Use Disorders (OUDs)

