subjects to process whatever emotions come up for the subject. If needed, for example if the subject is experiencing suicidal thoughts, further action will be taken if necessary as outlined above. Risks will also be reduced by having the research coordinator talk about their thoughts and feelings and craving after exposure to the drug use video.

- Procedure for Protecting Against Potential Risks:
Supervision: All of the scans will be done in the presence of constant supervision with experienced research staff always in attendance and in an institution specifically designed, equipped and functioning in support of these type studies. In the event that some serious medical complications could occur, the PET scan facilities are located in Wesley Woods Hospital on the Emory University campus and can provide immediate care. Confidentiality: All of the information obtained from patients is quoted by number and kept locked in confidential files. This information is available to study investigators. Risk-Benefit Ratio: The risks of participation in this study are small. These are outweighed by the potential benefit which a better understanding of the effects of OUDs could have for society.

PROTOCOL TITLE: Non-invasive Vagal Nerve Stimulation in Opioid Use Disorders

- Adverse events (AEs) are evaluated at each visit and reported to IRB using standard Emory IRB reporting guidelines. Serious adverse events (SAEs) (as defined by

CRF 312.32) are reported to the IRB using standard Emory IRB reporting guidelines. All AE and SAE reports will include a description of the event, severity, relationship to the study medication or procedures, any intervention required, and date of the resolution of the event (or otherwise listed as ongoing). SAEs include any fatal event, immediately life threatening event, permanently or significantly disabling event, event requiring prolonged inpatient hospitalization, or any congenital anomaly, and any other event that deems to result in a significant hazard, contraindication, side effect or precaution.

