9.0 Study Timelines*

9.1 Describe:

- The duration of an individual participant's participation in the study will be up to 3 study visits. We may also call them around 6 weeks after the visits to repeat a few questionnaires (Addiction Severity Index, SHAPS-C, COWS, NRS Pain Scale, the Subjective Units of Distress Scale, and the Visual Analogue Scale (VAS)) and see how they are doing. If they took a VNS device home then we will ask them about usage and remind them to return this to the study team.
- We expect to enroll all study participants within 2 years.
- The estimated date for the investigators to complete this study is 3/31/2025 but this depends on whether they are allowed to continue to the UH3 phase. This protocol contains details about the UG3 phase.

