13.0 Recruitment Methods

13.1 Subjects will be recruited from newspaper advertisements, websites (like Nextdoor) and/or fliers. We may also recruit from the general outpatient population at Emory and the data warehouse. Providers may also refer patients for the study. Participants in previous research studies who have opted in for future contact might also be invited. Once a potential subject is identified, a staff member will schedule a screening interview with them to ensure eligibility with study enrollment criteria. If done via phone, a verbal consent will be obtained by the study staff member. If eligible, subject will sign study consent at first visit before starting any research related procedures. If screening is not able to be done via phone then screening for eligibility will be done in-person.

13.2 Fliers will be used describing the study inclusion criteria and a few of the procedures.

13.3 For study 1:

Compensation ranges from \$75 to a total of up to \$250 for the study. We will also pay for parking, if needed, at each clinical visit.
Visit 2: \$175 (\$75 for the MRI and \$100 for the visit)
If subjects are given a VNS device to take home, they will get an

PROTOCOL TITLE: Non-invasive Vagal Nerve Stimulation in Opioid Use Disorders

additional \$75 upon successful return of the device using a prepaid return mailer.

For study 2:

Compensation ranges from \$75 to a total of up to \$350 for the study. We will also pay for parking, if needed, at each clinical visit.

If used as a backup participant: \$50 to cover time and transportation costs

Visit 2: \$150 (PET Day)

Visit 3: \$75 (MRI Day)

If subjects are given a VNS device to take home, they will get an additional \$75 upon successful return of the device using a prepaid return mailer.

Subjects could potentially participate in both studies.

A check will be mailed to the participant after participation is completed. Sometimes this can take 3-4 weeks for Emory to approve and cut the check. Another method of payment that will be offered is using the Greenphire ClinCard system.

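### No adverse-event assessment is scheduled after the last visit, and the 6-week call, conditional in section 9.1, has no adverse-event item even when a device went home

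*Combined protocol and SAP*

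**What the plan says.** Section 6.6 sets the routine for adverse events: "Adverse events (AEs) are evaluated at each visit and reported to IRB using standard Emory IRB reporting guidelines". It lists what an AE or SAE report must contain (description, severity, relationship, intervention, resolution date or ongoing status). The readable text gives no start or end to the collection period.

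On duration, the study summary (1.0) gives "2-3 study visits, 6 week follow up call". Section 9.1 says "The duration of an individual participant's participation in the study will be up to 3 study visits", and then "We may also call them around 6 weeks after the visits to repeat a few questionnaires". The repeated instruments cover addiction severity, capacity for pleasure, withdrawal, pain, distress and the visual analogue craving scale. The call is also meant to "see how they are doing. If they took a VNS device home then we will ask them about usage" and to remind participants to return the device. AEs and SAEs are not mentioned.

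The payment lists in 13.3 allow a device to go home in either study and to come back by prepaid mail. Section 5.2 says the devices are locked up and used only with the research coordinator supervising. On the drug-cue exposure, 6.6 warns: "Viewing videos about opioid use may result in an increase in opioid craving".

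**The concern.** AE evaluation is attached to visits. If exposure falls on a participant's last visit, the plan schedules an AE evaluation that day and none afterwards. If a device goes home, exposure can continue after the last visit, and the only listed device questions concern usage and return.

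The later safety machinery can act only on what has been reported. The independent monitor in 18.1 reviews subject-reported events every 6 months. The expedited reporting clocks in 6.6 start when the sponsor learns of an event. The study-wide stopping rule in 18.1 depends on adverse effects having been linked to the intervention. Without a scheduled question after the last visit, a delayed event enters this chain only by chance or on the participant's initiative. And if the call is made to some participants and not others, ascertainment will differ between them for reasons the plan does not control.

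**Working it through.** No power or sample-size figure bears on this point. The check compares the visit, call, payment and safety sections, with one piece of arithmetic on payments.

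**1. Which visit is last?** Sections 1.0 and 9.1 give 2-3 visits and up to 3 visits without splitting by study. Section 13.3 is the only place that does so.

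- Study #1: Visit 2 pays $75 (MRI) + $100 (visit) = $175. Device return pays $75. Total: $175 + $75 = $250, exactly the stated maximum.
- Study #2: Visit 2 (PET day) pays $150, Visit 3 (MRI day) $75 and device return $75. Total: $150 + $75 + $75 = $300. With the $50 backup payment, $300 + $50 = $350, again the stated maximum.

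Both lists close, so Study #1 has no paid visit after Visit 2. Section 6.3 has Study #1 participants stimulated while watching neutral and opioid videos, and Visit 2 is the only Study #1 visit listed with a payment. It is therefore reasonable to infer that exposure is at Visit 2 and that Visit 2 is the last visit. This is not proof: neither list assigns a payment to a Visit 1, so unpaid visits are possible.

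**2. What AE assessment follows exposure?**

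| | Study #1 (as inferred) | Study #2 |
|---|---|---|
| AE evaluation at the exposure visit | Yes, under 6.6 | Yes, under 6.6 |
| Later visit with AE evaluation | None listed | One (Visit 3), if visits run in listed order; interval not stated |
| AE/SAE item on the 6-week call | None listed | None listed |
| Possible home device use after the last visit | Yes | Yes |

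The interval from last visit to call is about 6 x 7 = 42 days.

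**3. Is the call firm?** Section 1.0 lists it without qualification; 9.1 makes it conditional. The two do not agree.

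**4. Does the call content substitute for AE collection?** The scales would show craving, withdrawal, pain and distress at the time of the call, and the open enquiry could bring other events to light. But a scale score is not an AE record of the kind 6.6 requires, and no rule turns an answer on the call into one.

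**5. Is home use consistent with 5.2?** No. Section 5.2 confines use to supervised study purposes, while 9.1 and 13.3 provide for a device leaving with the participant. These sections must be reconciled.

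**The case against.** The strongest reply is that the plan does not leave participants unobserved. AEs are evaluated on the exposure day itself, and staff debrief participants about craving after the videos. Sections 6.6 and 15.1 describe stimulation effects as ones that resolve when treatment stops, or usually do so straight away. Several routes are not tied to visits: SAE and IND reporting (6.6), immediate discussion of candidate safety events with the independent monitor and reporting of unanticipated events to the IRB (18.1), and the instruction to call a clinician or go to the Emergency Room (24.1). The call, if made, measures craving, withdrawal and distress directly.

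Most of this stands, and it rules out several stronger readings that a reader might infer:

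- That nothing is collected after the Study #1 exposure visit. The call's scales and open enquiry contradict this.
- That half of the 40 planned completers have no AE evaluation after exposure. The exposure visit carries its own evaluation, and 13.3 lets people join both studies, so the two groups of 20 may overlap.
- That collection stops just as the risk period starts. The documents do not place the risk period there, and the statement in 15.2 about unevaluated long-term effects concerns chronic use of VNS.
- That the decision to move to the UH3 phase rests on these AE data. Section 2.1 refers only to meeting the goals of the UG3 phase and does not define them as safety data.

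What the reply does not supply is active ascertainment after the last visit. The other routes are unscheduled: they need someone to volunteer the event or staff to come across it.

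**Conclusion.** The concern holds in a limited form. As written, the plan has no scheduled AE or SAE enquiry after the last visit, and none on the one later contact it describes. This applies to both studies and includes any period of home device use. Delayed events reach the IRB and the independent monitor only if volunteered or found incidentally.

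The size is an interval of about 6 weeks without scheduled AE enquiry. The number of events missed cannot be estimated from the documents. That the Study #1 gap begins directly after the stimulation and video visit rests on the payment schedule and is an inference. The absence of a defined collection period, the conflict between 1.0 and 9.1, and the lack of an AE item on the call are read directly from the text. No safety endpoint is planned, so this is a worthwhile and inexpensive improvement to safety capture rather than a threat to the primary analysis.

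**What to change.** - In 9.1, make the call firm (will rather than may), so that it agrees with 1.0.
- In 6.6 and 9.1, state that AEs and SAEs are collected from first exposure through that call.
- Add to the call a direct AE/SAE question covering the whole time since the last visit, including any home device use.
- Record the answers as AEs with the content 6.6 already requires, and include them in the independent monitor's review.
- Reconcile home device use in 9.1 and 13.3 with the supervised-use statement in 5.2.

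The cost is protocol wording and a short addition to a contact already described; no new visit is needed. Staff must attempt the call for every participant, and reported AE counts may rise because events are being asked about.
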